Official Title of the study:

The Impact of Different Methods of Oral Hygiene on Incidence of Ventilator Associated Pneumonia in PICU

Document date:

11/6/2024

What is already known on this subject? What does this study add?

Ventilator associated pneumonia (VAP) is a potentially serious complication in critically ill children who are admitted to the Pediatric intensive care unit (PICU).

The Institute for Healthcare Improvement (IHI) introduced a “bundle” that collectively and reliably performs a set of evidence-based practices, which have been proven to improve patient outcomes.

The VAP bundle is composed of five major interventions which include daily oral care with chlorhexidine. (*R. Resar et al., 2005*)

In this study we will assess the effects of different methods of oral care on incidence of VAP in critically ill patients who will be admitted & mechanically ventilated in PICU Ain Shams University Children hospital and will determine its impact on length of PICU stay, days on mechanical ventilation and mortality.

1. Introduction

Ventilator-associated pneumonia (VAP) is defined by the Center for Disease Control and Prevention (CDC) and National Healthcare Safety Network (NHSN) as new and persistent radiographic infiltrates and worsening gas exchange in children who are ventilated for at least 48 hours and who exhibit at least 3 of the following criteria: temperature instability with no other recognized cause, leukopenia, change in the characteristic of respiratory secretions, respiratory distress and bradycardia or tachycardia (*Semenkovich et al., 2019*).

VAP is the second most common hospital-acquired infection among PICU patients. It accounts for 7% to 32% of healthcare-associated infections and 10% of all pediatric device-related infections reported to NHSN. (*Bhattacharya et al., 2023*).

The hypothesis of oral care regimes in PICU is to decrease infectious, inflammatory, and painful symptoms that occur in critically ill patients: mechanically (by removing the biofilm through brushing the teeth and tongue) and pharmacologically (by using antiseptic agents). (*Gomaa et al., 2017*).

Several studies were carried out in different PICUs using different oral hygiene regimes. These studies concerned with the effect of application of these regimes on the prevalence of VAP, mortality, and duration of mechanical ventilation. Most studies evaluated chlorhexidine (CHX) based regimes and its effect on incidence of VAP.

In a Cochrane Library systematic review on oral care strategies for critically ill patients to prevent VAP, the authors concluded that antiseptics and tooth brushing may be more effective than standard oral health hygiene strategies in reducing the incidence of VAP and the length of PICU stay (*Gregorczyk-Maga et al., 2023*).

2.Aim

1. To determine incidence of VAP in patients who will be admitted to PICU with routine oral hygiene in comparison to those using brushing and chlorhexidine.
2. To detect the impact of different methods of oral hygiene on mechanically ventilated patients regarding duration of mechanical ventilation, length of PICU stay and mortality rate.

3.Patients and Methods

- **Study Setting:** The study will be carried out in Ain-Shams University Children hospital, Pediatric Intensive Care Units (PICUs).
- **Study Design:** Randomized Control Trial.
- **Study Period:** until fulfillment of the study.
- **Ethical Considerations:** This study will start after approval of the " Research Ethics Committee" of Ain- Shams University Hospitals. Written consent will be obtained from the legal guardians of the patient. The guardians have the right to withdraw from the study at any time.
- **Study Population:** any patients aged from 18 months to 16 years admitted to PICU fulfilling inclusion criteria.
- **Inclusion criteria:**
 - Patients who will be on invasive mechanical ventilation.
 - Dentate patient.
 - Aged 18 months -16 years old.
- **Exclusion criteria:**
 - Patients with primary Immune deficiency.
 - Coagulation disorders.
 - Jaw fractures.
- **Sample Size:** 118 pediatric patients.
Based on the results of (**Vidal et al. 2017**) showing that among patients admitted to intensive care unit, the incidence of ventilator associated pneumonia in patients on oral care involving tooth brushing with chlorhexidine was lower than in patients on oral hygiene by chlorhexidine swab only (37,8% and 62,2% respectively).

4.Methodology:

The following assessment will be done to each patient. 1-

History:

- Demographic data: (name, age, sex).
- Medical diagnosis on admission.
- Comorbidities.
- Need for inotropic support.
- Day of worsening of respiratory symptoms after ventilation.
- Fate

Risk factors:

- Days in (PICU) until intubation. ○ Days on mechanical ventilation (MV) until infection.
- Potential risk factors: inhaled bronchodilators, proton pump inhibitors, neuromuscular blockers (doses & duration).
- Route of mechanical ventilation: Nasotracheal, endotracheal, tracheostomy. ○ Method of nutrition: Nasogastric tube, parenteral, gastrostomy.
- The antibiotic used (name, including duration, need to switch) .

1- General examination: Routine monitoring of Temperature, Heart Rate, Respiratory Rate, Blood Pressure.

Physical examination: Chest auscultation.

Then patients will be divided into 2 groups (59 patients in each group).

• **Sample Grouping:** VAP bundle will be applied in both groups

Intervention group: Brushing plus 0.12% chlorhexidine mouthwash.

All patients will be placed in semi recumbent position (head up position by elevating the head of their bed 30 to 45degree angle). Mouth care will be performed at least 5 minutes in each session as long as the patient is on invasive mechanical ventilation.

Patient will receive brushing by soft tooth brush and toothpaste three times daily using the Bass technique (toothbrush should be positioned at a 45 degree angle with a firm yet gentle pressure , brush back and forth or use a circular motion 15 to 20 times before moving to the next area) for one minute, plus application of 0.12% chlorhexidine mouthwash to a swab on the oral mucosa, teeth, gums, hard palate, and tongue, followed by 20 mL of normal saline , the procedure will be finished with hypo pharyngeal suctioning.

Control group: routine PICU oral care which is rinsing mouth with 0.12% chlorhexidine that is applied to a swab and rubbing it on the surface of the tongue, gum and mucosa followed by 20 mL of normal saline, three times daily, the procedure will be finished with hypo pharyngeal suctioning.

Oral Care protocol:

- Pediatric dentist will be assigned to train the PICU nurses to follow the proper Oral Care Protocol including brushing technique, mouth rinses and intraoral massaging.

2- Investigations:

a) Laboratory:

- I. CBC with differential,
- II. C- reactive Protein (CRP),
- III. Venous blood gases (VBG),
- IV. Bio-fire if available, Sputum culture, Blood culture.

The first day, the data will be collected as the pre-test data. Then the second, third- and fourth-days data will be considered as the first, second and third post-test data sets respectively. The sputum cultures will be collected on the fifth day.

b) Radiology: initial Chest x-ray on admission and follow up (to detect development of new infiltration or consolidation).

Official Title of the study:

The Impact of Different Methods of Oral Hygiene on Incidence of Ventilator Associated Pneumonia in PICU

Unique Protocol Id

FMASU MS407 /2024

Document date:

11/6/2024

Objectives:

Primary objective:

To determine incidence of VAP in patients who will be admitted to PICU with routine oral hygiene in comparison to those using brushing and chlorhexidine.

Secondary objective:

To detect the impact of different methods of oral hygiene on mechanically ventilated patients regarding duration of mechanical ventilation, length of PICU stay and mortality rate.

Arms:

Arm 1: Toothbrushing + Chlorhexidine

Arm 2: Routine Oral Care + Chlorhexidine

Outcomes:

Primary Outcome:

- **Measure:** Incidence of ventilator-associated pneumonia (VAP)
- **Time Frame:** Until first occurrence of VAP during mechanical ventilation
- **Description:** VAP will be diagnosed according to standard clinical and microbiological criteria.

Secondary Outcomes:

1. **Measure:** Duration of mechanical ventilation
 - **Time Frame:** During PICU stay
 - **Description:** Number of days each patient remains on mechanical ventilation.
2. **Measure:** Length of PICU stay
 - **Time Frame:** During PICU stay
 - **Description:** Total days from PICU admission to discharge.
3. **Measure:** Mortality rate
 - **Time Frame:** During PICU stay
 - **Description:** Number of deaths among enrolled patients during the PICU stay.

Statistical analysis:

Statistical analysis is performed by SPSS in general (version 20), while Microsoft office Excel is used for data handling and graphical presentation. Quantitative variables is described by

the Mean, Standard Deviation (SD), the Range (Minimum – Maximum), Standard Error (SE) ,95% confidence interval of the mean, Coefficient of Variation (CV), Median and Inter Quartile Range (IQR).

The tests used :

1. Chi-square test

For categorical variables, to compare between different groups.

2. Mann Whitney test

For abnormally distributed quantitative variables, to compare between two studied groups.

3. Two sample T-test

A two-sample t-test is a statistical test used to determine whether the means of two independent groups are significantly different from each other. It is often used in scientific research to compare the means of two groups of data.

4. p-values

Indicate the statistical significance of the relationship. A p-value less than 0.05 is considered statistically significant, indicating that the relationship is unlikely to be due to chance.

Handling missing data:

Using complete data analysis until VAP occurrence.

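### Toothbrushing is visible at the bedside and nothing keeps those who classify VAP unaware of the arm, so differential calling can bias the primary comparison

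*SAP*

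**What the plan says.** **Arms.** Under Sample Grouping in the Protocol, for the intervention group, "Patient will receive brushing by soft tooth brush and toothpaste three times daily using the Bass technique", together with chlorhexidine. The control group receives "routine PICU oral care which is rinsing mouth with 0.12% chlorhexidine that is applied to a swab", also three times daily. No sham brushing is described. PICU nurses are trained to follow the oral care protocol.

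**Outcome.** The SAP, under Primary Outcome, says "VAP will be diagnosed according to standard clinical and microbiological criteria" and adds no list, decision rule or assessor. The only explicit definition is the CDC/NHSN summary in the Protocol's Introduction. It requires new and persistent infiltrates, worsening gas exchange and at least three further signs. Among those signs are "change in the characteristic of respiratory secretions, respiratory distress and bradycardia or tachycardia". The SAP does not state that this is the trial definition.

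**Sources of evidence.** Under Investigations, the Protocol lists "initial Chest x-ray on admission and follow up (to detect development of new infiltration or consolidation") with no timetable and no named reader, and "Bio-fire if available, Sputum culture, Blood culture". One element has a stated day: "The sputum cultures will be collected on the fifth day". Blood counts, CRP, blood gases and lavage microbiology are also collected.

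**Masking.** Neither document mentions blinding, masking, an independent reader or adjudication. The design is given only as a randomised controlled trial.

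**The concern.** Three features combine. Staff can see which children are brushed. The outcome involves judgement: whether secretions have changed, whether there is respiratory distress, whether an infiltrate is new. And nothing separates knowledge of the arm from the decision that a child has VAP.

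The decision to look can also depend on the arm, because follow-up films have no schedule and one laboratory test depends on availability. A lower threshold for imaging or for calling VAP in one arm would raise the recorded incidence there without any difference in disease.

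VAP incidence is the only primary outcome. The planned chi-square test and the complete-data rule take the recorded diagnosis as given, so neither would show such a difference for what it is.

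**Working it through.** The plan gives no figure on this point to reproduce, and its sample size is not in dispute here. The calculation asks how far modest differences in calling could move the false-positive rate.

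**Inputs from the documents:** 59 children per arm (Protocol, Sample Grouping); chi-square test and significance at p<0.05 (SAP, Statistical analysis); planning control rate 62.2% (Protocol, Sample Size).

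**Assumptions:** no true effect; true VAP risk p in both arms, 20% to 50%, with 62.2% added as a check; two-sided test without continuity correction; calling error d of 2%, 5% or 10%. The documents give no error rates.

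**Formulas.**
- Over-calling in control only: recorded rates p + (1−p)d and p; gap (1−p)d.
- Under-calling with brushing only: recorded rates p and p(1−d); gap pd.
- Both: recorded rates p + (1−p)d and p(1−d); gap (1−p)d + pd = d.

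Example with p = 30%, d = 5%, both errors: control 0.30 + 0.70 × 0.05 = 0.335; brushing 0.30 × 0.95 = 0.285; gap 0.05. That is 0.05 × 59 ≈ 3 children. At d = 10% the gap is about 6 children.

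The rejection probability is the sum, over all pairs of case counts from 0 to 59, of the two binomial probabilities multiplied together wherever the chi-square test gives p<0.05.

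| True risk | No error | 5% control only | 5% brushing only | 5% both | 10% control only | 10% brushing only | 10% both |
|---|---|---|---|---|---|---|---|
| 20% | 5.3% | 8.5% | 5.5% | 10.5% | 17.8% | 6.2% | 25.8% |
| 30% | 5.2% | 7.1% | 5.6% | 9.2% | 12.7% | 6.7% | 21.6% |
| 40% | 4.9% | 6.3% | 5.5% | 8.5% | 10.2% | 7.2% | 19.7% |
| 50% | 5.3% | 6.1% | 6.1% | 8.8% | 8.8% | 8.8% | 19.9% |
| 62.2% | 4.9% | 5.4% | 6.3% | 8.5% | 7.0% | 10.5% | 19.7% |

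With 2% errors in both arms the result is 5.5% to 6.2%.

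The SAP does not say whether a continuity correction applies. With one, the no-error rate is about 3%, and over the same risks the two-arm errors give about 6% (d = 5%) and 15% to 18% (d = 10%). The levels are lower, but the rise from the starting point is of similar proportion.

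**The case against.** The strongest reply is that much of the evidence is objective. The SAP names microbiological as well as clinical criteria, which most naturally means both. The Introduction's definition also asks for worsening gas exchange, and its list includes temperature and leukopenia. Sputum culture has one stated day for everyone, which limits arm-dependent sampling. This stands as mitigation. It does not close the gap, because no rule says how the components combine or that a positive culture is required, and the SAP never adopts the Introduction's list.

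The second reply concerns size. Errors in both arms, each favouring brushing, are a stacked scenario, and nothing in the documents supports those rates or that direction. This also stands, which is why single-arm and 2% errors are shown beside it.

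Four stronger readings are tempting, but the documents do not support them:
- A reader might infer that the trial will be biased in favour of brushing. The documents show an opening for bias, not its direction.
- A reader might take "Physical examination: Chest auscultation" as a further subjective VAP criterion. It stands in the assessment placed before children are divided into groups, and no text makes it part of the diagnosis.
- A reader might conclude that no later analysis could help. Cultures, lavage and laboratory results are collected, and an analysis restricted to them could expose or limit the bias, though not abolish it.
- A reader might assume that masking the outcome would be complete or that a masked film reader already exists. Bedside signs would still be recorded by staff who know the arm, and the documents do not say who reads the films.

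**Conclusion.** The concern holds as a risk, not as a demonstrated bias. The arms are distinguishable at the bedside, the primary outcome leaves room for judgement, and the plan does not keep those who classify VAP unaware of the arm.

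How much this matters depends on error rates that the documents do not give. Calling errors of about 2% would be unimportant. Errors of 5% to 10% in one arm give modest to appreciable inflation, and opposite 10% errors in both arms would produce a false positive in roughly one trial in four or five. Because masked classification of data already being collected costs little, the plan should include it.

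**What to change.** 1. State that the VAP classification used in the primary analysis is made by an existing member of the study team who does not know the arm. That person applies written criteria to a data sheet holding films, cultures, laboratory results and recorded signs, with allocation and oral-care records removed.
2. Leave the arm off imaging and culture requests.
3. State that the indications for follow-up films and cultures are the same in both arms. What those indications are is a clinical matter for the investigators.
4. Add a sensitivity analysis of the primary outcome restricted to objective components already collected: culture or lavage, laboratory results and the masked film read.
5. Say in the report that masking was partial, because bedside signs were recorded by staff who knew the arm.

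The cost is protocol and SAP wording, a masked data sheet and minor logistics. Sample size and treatment do not change. If no existing team member can be kept unaware of the arm, the masked requests and the sensitivity analysis on objective components can still be adopted without extra staff.

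### No harm that toothbrushing could cause is an outcome or a collected field, and the ventilation day count has no rule for unplanned extubation, reintubation or death

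*SAP*

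**What the plan says.** The protocol (section 4, Sample Grouping) gives both arms the VAP bundle. Both also have mouth care three times daily with a 0.12% chlorhexidine swab, 20 mL of saline and closing hypopharyngeal suction. The intervention arm adds brushing: "Patient will receive brushing by soft tooth brush and toothpaste three times daily using the Bass technique", for one minute. Under the intervention heading the protocol also says "Mouth care will be performed at least 5 minutes in each session as long as the patient is on invasive mechanical ventilation".

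The SAP's primary outcome is VAP incidence. The secondary objective compares the arms "regarding duration of mechanical ventilation, length of PICU stay and mortality rate". The three secondary outcomes are defined as:

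- duration of ventilation: "Number of days each patient remains on mechanical ventilation";
- length of PICU stay: "Total days from PICU admission to discharge";
- mortality: "Number of deaths among enrolled patients during the PICU stay".

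The protocol's data list (section 4) covers history, risk factors, examination, laboratory tests, chest radiology and microbiology. The fields nearest to a harm are the day respiratory symptoms worsened, the route of ventilation and the patient's fate. The exclusion criteria include "Coagulation disorders" and jaw fractures, with no reason given. Neither document has an adverse-event section.

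**The concern.** The trial tests a mechanical procedure in the mouths of ventilated children. A unit deciding whether to adopt brushing would want to know whether it lowers VAP and also whether it displaces tubes, causes bleeding, or injures mucosa or teeth. As planned, the trial can answer the first question and, apart from all-cause death, has no data on the second. Because the arms share most of the rest of the mouth-care session, a count of such events by arm would bear directly on brushing.

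The duration outcome is a secondary matter. It is a raw day count with no stated rule for unplanned extubation, reintubation or death. Without such a rule, an episode that ended badly could look the same as one that ended well and early.

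**Working it through.** **1. Is any brushing-related harm captured?** Each candidate event set against the SAP outcomes and the protocol data list:

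| Event | SAP outcome | Protocol field |
|---|---|---|
| Unplanned extubation | none | none (route of ventilation only) |
| Oral bleeding | none | none (coagulation disorders are an entry exclusion only) |
| Mucosal or dental injury | none | none |
| Death from any cause | PICU mortality | fate, with no link to mouth care |

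The first three rows are empty in both documents.

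**2. What could a count show with 59 per arm?** The arm size is from protocol section 4; the number of events is hypothetical.

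- One arm, no events. The one-sided 95% upper bound p solves (1 − p)^59 = 0.05, so p = 1 − 0.05^(1/59) = 0.0495, about 5%.
- Contrast between arms, two-sided Fisher test. For 0 v 5 events, p = 2 × C(59,5)/C(118,5) = 0.057. For 0 v 6, p = 2 × C(59,6)/C(118,6) = 0.027. Six of 59 is 10.2%, so with none in the other arm an excess of about 10% is needed to reach 0.05.

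The count can bound a risk within an arm, but it is not a powered comparison.

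**3. How does the day count treat a lost tube?** The wording of the definition and the SAP's time frame (during PICU stay) give four cases:

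- Reintubated, later days summed: the total need not fall.
- Reintubated, counting stops at first extubation: the total is too short.
- Not reintubated, child survives: the total is short, and correctly so, because the child did leave ventilation.
- Child dies: the total is short for a bad reason, whatever caused the death.

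The SAP does not say which of the first two applies, or how death enters.

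**4. How large could the effect be?** The documents give no event rate, so this is an illustration on assumed inputs only. It uses gamma-distributed ventilation days (mean 8, SD 6), 59 per arm, no true benefit, tube loss in the brushing arm only, a Mann-Whitney test at two-sided 0.05, and 3,000 simulated trials. Differences are brushing minus control. The summed rule adds one day per event.

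| Tube loss, brushing arm | Mean difference, count stops at tube loss | Chance of false favourable result | Mean difference, days summed | Chance of false favourable result |
|---|---|---|---|---|
| 0% | about 0 | 2.5% | about 0 | 2.5% |
| 5% | −0.2 days | 4% | +0.05 days | 2.2% |
| 10% | −0.4 days | 5% | +0.1 days | 1.3% |
| 20% | −0.8 days | 13% | +0.2 days | 1.4% |

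The direction depends on the counting rule, and the shift is small unless tube loss is frequent.

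**The case against.** A reader might infer that a tube dislodged during brushing would be scored as a shorter, better ventilation time. The documents do not support that. On a plain reading of the definition a reintubated child goes on accruing days, and a surviving child who is not reintubated has truly left ventilation and exposure to VAP. A fatal dislodgement would shorten the count but would also appear under mortality. This objection stands. What remains is that the counting rule is unwritten and that death shortens the count.

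A reader might also count three extra procedures near the airway each day. The protocol does not support this either. Control children have the same number of sessions, with swabbing, saline and suction, and the natural reading is that a minute of brushing is added to a session both arms have.

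Nor can the exclusions for coagulation disorders and jaw fractures be taken as showing that the investigators expect bleeding or injury, since the protocol states no reason for them.

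The protocol has safeguards: a soft brush, and training of the nurses by a pediatric dentist. These may lower the risk, but they do not measure it.

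Finally, 59 per arm is too few to compare uncommon harms formally. That is correct. It is a reason to report the events descriptively with confidence intervals; it does not justify leaving them uncollected.

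**Conclusion.** The point holds as a gap in what is collected. Neither document has an outcome or field for unplanned extubation, oral bleeding, or mucosal or dental injury, so as written the trial can report efficacy and all-cause death but no other harm of brushing. This rests on the text alone and needs no assumption.

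The duration point is narrower. The raw count could mislead if counting stops at first extubation or if the child dies; it does not necessarily do so. The size of any bias is unknown, and the simulated shifts above rest on assumed durations and tube-loss rates. No figure in the plan changes, and the primary analysis and sample size are unaffected.

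**What to change.** Add to the SAP's secondary outcomes, by arm and per ventilated day:

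- unplanned extubation, with its relation to a mouth-care session and whether the child was reintubated;
- oral bleeding;
- oral mucosal or dental injury.

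Record all three on one identical mouth-care chart line in both arms, for as long as invasive ventilation lasts. State that recording continues after VAP, since the SAP's missing-data rule runs only until VAP occurs. Report both the number of events and the number of children with at least one, with confidence intervals and as description only.

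In the duration outcome, state that days after reintubation are added to the same child's total. Identify the episodes ended by unplanned extubation or death when the comparison is reported.

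The cost is one chart line, one descriptive table and two sentences in the SAP. The downside is that nurses cannot be blinded to brushing, so events may be recorded more fully in that arm. The identical form in both arms limits this but does not remove it, and the report should say so.

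### Length of PICU stay is counted from admission, so days before intubation add noise to this secondary comparison: a minor, cheaply fixed loss of precision

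*SAP*

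**What the plan says.** The SAP, under Secondary Outcomes item 2, measures length of PICU stay as "Total days from PICU admission to discharge". For quantitative outcomes its list of tests names only the Mann-Whitney test and the two-sample t-test. No covariate adjustment is planned.

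The protocol ties oral care to the ventilated period. The intervention-group text under Sample Grouping states: "Mouth care will be performed at least 5 minutes in each session as long as the patient is on invasive mechanical ventilation". The inclusion criterion is "Patients who will be on invasive mechanical ventilation". It does not require intubation on the day of admission.

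Section 4 of the protocol (Methodology, Risk factors) lists "Days in (PICU) until intubation" among the items recorded for each patient. The SAP does not use this item.

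The design is a "Randomized Control Trial" of "118 pediatric patients", 59 per group. Neither document says when randomisation takes place relative to admission or intubation.

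**The concern.** The secondary objective asks what the oral-care method does to ventilated children, and PICU stay is one of its three measures. A child intubated several days after admission brings those days into the outcome, yet they were over before the assigned care could act. They carry no information about the treatment. Their spread between children widens the standard error of the comparison.

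What is at stake is the chance of detecting a real difference in stay in a trial with only 59 children per arm. A difference expressed as a percentage of total stay would also look smaller than the same difference expressed as a percentage of the stay that the care could influence.

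**Working it through.** **Inputs from the documents.** 59 children per arm; significance at p < 0.05, taken here as two-sided because the SAP does not say; unadjusted tests. The sample size rests on VAP incidence. No mean, SD or target difference for stay is given, so there is no planned figure for stay to reproduce.

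**Assumptions.** Days before and after intubation are independent. Let r be the SD of pre-intubation days divided by the SD of days from intubation to discharge. The documents give no value for r, so a range is shown.

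**Step 1: variance.** Stay from admission is the sum of the two periods, so its variance is (1 + r²) times that of stay from intubation. The effective number per arm is 59/(1 + r²).

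**Step 2: power.** Take a difference detectable with 80% power when stay is counted from intubation. The standardised signal is then 1.960 + 0.842 = 2.802. Counting from admission divides it by √(1 + r²), and power is Φ(2.802/√(1 + r²) − 1.960).

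| r | 1 + r² | SD multiplier | Effective n per arm | Power |
|---|---|---|---|---|
| 0.1 | 1.010 | 1.005 | 58.4 | 79.6% |
| 0.25 | 1.063 | 1.031 | 55.5 | 77.6% |
| 0.5 | 1.250 | 1.118 | 47.2 | 70.7% |
| 0.75 | 1.563 | 1.250 | 37.8 | 61.1% |
| 1 | 2.000 | 1.414 | 29.5 | 50.8% |

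For r = 0.5: 2.802/1.118 = 2.506; 2.506 − 1.960 = 0.546; Φ(0.546) = 0.707.

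**Step 3: bias, by simulation.** 3,000 trials were simulated with 59 children per arm. Days after intubation were gamma with shape 2 and means of 8 versus 12. Pre-intubation days were exponential and unrelated to arm. The average post-intubation variance is (8²/2 + 12²/2)/2 = 52, an SD of 7.2. Pre-intubation means of 1, 2 and 4 days therefore correspond to r of about 0.14, 0.28 and 0.55.

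| Mean pre-intubation days | Mean difference, from intubation / from admission | t-test power, from intubation / from admission / from admission adjusted | Mann-Whitney power, from intubation / from admission |
|---|---|---|---|
| 1 | −4.00 / −4.00 | 0.87 / 0.86 / 0.86 | 0.81 / 0.79 |
| 2 | −4.04 / −4.04 | 0.87 / 0.84 / 0.87 | 0.81 / 0.77 |
| 4 | −4.00 / −4.01 | 0.86 / 0.75 / 0.86 | 0.80 / 0.69 |

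The adjusted analysis is a linear regression of stay from admission on arm and pre-intubation days. The mean difference is the same with either clock. Only precision changes, and adjustment restores it.

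**Step 4: relative size.** With 4 pre-intubation days, 8 versus 12 becomes 12 versus 16. The difference is still 4 days, but the relative reduction falls from 4/12 = 33% to 4/16 = 25%.

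**The case against.** The strongest reply is that nothing here is biased. In a randomised trial, days completed before randomisation are balanced in expectation. A chance imbalance in them is ordinary sampling error, which the standard error already covers. The type I error is not affected. This stands. A reader might infer that the definition hides or distorts the effect of brushing; with randomisation after intubation, the documents do not support that.

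The second reply is that the loss may be trivial. Recording pre-intubation days shows that they can differ between children. It does not show that they are long or variable. If most children are intubated at or near admission, little is lost. This also stands, and it is why only a range can be given.

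The third reply is that admission to discharge is the ordinary meaning of PICU stay and is unambiguous. That is fair, and adjustment offers a way to keep it.

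A reader might also infer that duration of ventilation has the same fault because its starting point is not spelled out. That is not shown. Days before intubation cannot enter a count of ventilated days, and neither document indicates that ventilated days precede randomisation. The secondary objective therefore has one duration measure without this problem.

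**Conclusion.** The point holds as a minor precision issue on one secondary outcome. The stay clock starts at admission, the assigned care belongs to the ventilated period, and the planned tests ignore an item the protocol already records.

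The size is unknown. From a starting power of 80%, the loss is about 2 percentage points or less for r up to 0.25, about 9 points at r = 0.5 and about 19 points at r = 0.75. These figures assume that the two periods are independent and that pre-intubation days are unrelated to arm. The second assumption follows from randomisation if it takes place after intubation, but the documents do not state that timing. The primary outcome is not affected. This is a cheap improvement, not a flaw that threatens the trial's conclusions.

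**What to change.** In the SAP:

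- State when randomisation takes place relative to admission and intubation.
- Compare PICU days from randomisation to discharge. If the randomisation date is not recorded and randomisation takes place at intubation, count from intubation, using the pre-intubation item already collected.
- Alternatively, keep stay from admission as the outcome and adjust for pre-intubation days, for example by linear regression on arm and those days. This is sound only if those days precede randomisation.
- Report total stay from admission descriptively, and show pre-intubation days by arm with the baseline characteristics.
- Choose one of these as the analysis before outcome data are examined.

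**Cost.** A few sentences in the SAP and no extra patients. No allocation date appears among the items the protocol lists, so counting from randomisation may need that date added to the record; counting from intubation or adjusting needs no new item. The drawback of a later clock is that the compared outcome is no longer the conventional total stay, which is why the total should still be reported.
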